10.6.2.2. Handling of Partial Dates

Element	Reporting Detail
Concomitant Medications	
 • Partial dates for any concomitant medications recorded in the CRF will be imputed using the following convention: 
 ○ If the partial date is a start date, a '01' will be used for the day and 'Jan' will be used for the month ○ If the partial date is a stop date, a '28/29/30/31' will be used for the day (dependent on the month and year) and 'Dec' will be used for the month. • The recorded partial date will be displayed in listings.
Adverse Events	
 • Any partial dates for adverse events will be raised to data management. If the full date cannot be ascertained, the following assumptions will be made: 
 ○ If the partial date is a start date, a '01' will be used for the day and 'Jan' will be used for the month. ○ However, if these results in a date prior to Week 1 Day 1 and the event could possibly have occurred during treatment from the partial information, then the Week 1 Day 1 date will be assumed to be the start date. ○ The AE will then be considered to start on-treatment (worst case). ○ If the partial date is a stop date, a '28/29/30/31' will be used for the day (dependent on the month and year) and 'Dec' will be used for the month. • The recorded partial date will be displayed in listings.

10.6.2.3. Handling of Missing Data for Statistical Analysis

Element	Reporting Detail
Responder	
 • Subjects with a missing baseline will have responder status as missing • Subjects with missing post-baseline data at a time point and a subsequent non-missing assessment will not be considered a responder or non-responder but will be left as missing at that time point • Subjects with a missing post-baseline assessment with no subsequent non-missing assessments will be considered a non-responder for that and all subsequent time points. • Subjects with a baseline but all missing post-baseline data will be considered a non-responder at all time points.

10.7. Appendix 7: Abbreviations & Trade Marks

10.7.1. Abbreviations

Abbreviation	Description
A&R	Analysis and Reporting
ADaM	Analysis Data Model
AE	Adverse Event
AESI	Adverse Event of Special Interest
ANCOVA	Analysis of Covariance
ASE	All Subjects Enrolled
ATC	Anatomical-Therapeutic-Chemical
BDI	Baseline Dyspnea Index
CAT	COPD Assessment Test
CDISC	Clinical Data Interchange Standards Consortium
CI	Confidence Interval
COPD	Chronic Obstructive Pulmonary Disease
CSR	Clinical Study Report
CV	Cardiovascular
DBF	Database Freeze
DM	Data Management
DPI	Dry Powder Inhaler
eCRF	Electronic Case Record Form
EXACT	Exacerbations of Chronic Pulmonary Disease Tool
FEV ₁	Forced Expiratory Volume in One Second
FVC	Forced Vital Capacity
GCSP	Global Clinical Safety and Pharmacovigilance
GOLD	Global Initiative for Chronic Obstructive Lung Disease
GSK	GlaxoSmithKline
GUI	Guidance
IA	Interim Analysis
ICS	Inhaled Corticosteroid
IDSL	Integrated Data Standards Library
IMMS	International Modules Management System
IP	Investigational Product
ITT	Intent-To-Treat
KR	Kenwood Roger
LRTI	Lower Respiratory Tract Infection
LS	Least-square
mcg	Microgram
MMRM	Mixed Model Repeated Measures
PD	Protocol Deviation
PDMP	Protocol Deviation Management Plan
PRO	Patient Reported Outcomes
QD	Once Daily
QoL	Quality of Life

Abbreviation	Description
RAMOS	Randomization & Medication Ordering System
RAP	Reporting & Analysis Plan
RMC	Respiratory Medication Classification
RTF	Rich Text Format
SAC	Statistical Analysis Complete
SAE	Serious Adverse Event
SAL	Salmeterol
SDL	Source Data Lock
SDTM	Study Data Tabulation Model
SE	Standard Error
SGRQ	St. George Respiratory Questionnaire
SGRQ-C	SGRQ for COPD patients
SI	System Independent
SMQ	Standardized MedDRA Query
SOC	System Organ Class
SOP	Standard Operation Procedure
TDI	Transition Dyspnea Index
TFL	Tables, Figures & Listings
UMEC	Umeclidinium Bromide (GSK573719)
VI	Vilanterol Trifenatate

10.7.2. Trademarks

Trademarks of the GlaxoSmithKline Group of Companies
DISKUS
ELLIPTA

Trademarks not owned by the GlaxoSmithKline Group of Companies
SAS

10.8. Appendix 8: List of Data Displays

10.8.1. Data Display Numbering

The following numbering will be applied for RAP generated displays:

Section	Tables	Figures
Study Population	1.1 to 1.n	1.1 to 1.n
Efficacy	2.1 to 2.n	2.1 to 2.n
Safety	3.1 to 3.n	3.1 to 3.n
Section	Listings	
ICH Listings	1 to x	
Other Listings	y to z	

10.8.2. Deliverables

Delivery	Description
SAC	Final Statistical Analysis Complete.

10.8.3. Study Population Tables

Study Population Tables				
No.	Popu- lation	Title	Programming Note	Deliverable
Subject Disposition				
1.1	ASE	Summary of Study Populations		SAC
1.2	ASE	Summary of Screen Failures and Run-in failures		SAC
1.3	ITT	Summary of Attendance/Telephone Contact at Each Visit		SAC
1.4	ITT	Summary of Completion and Premature Discontinuation of Study Treatment		SAC
1.5	ITT	Summary of Study Completion and Withdrawal		SAC
1.6	ITT	Summary of Number of Subjects by Geographical Region, Country and Center		SAC
1.7	ASE	Summary of Inclusion/ Exclusion/ Randomization Criteria Deviations for Screen or Run-in failures		SAC
1.8	ITT	Summary of Inclusion/ Exclusion/ Randomization Criteria Deviations		SAC
1.9	ITT	Summary of Important Protocol Deviations		SAC
Demography				
1.10	ITT	Summary of Demographic Characteristics		SAC
1.11	ITT	Summary of Race and Racial Combinations		SAC
1.12	ITT	Summary of Race and Racial Combination Details		SAC
Medical Condition & Concomitant Medications				
1.13	ITT	Summary of Current Medical Conditions		SAC
1.14	ITT	Summary of Past Medical Conditions		SAC
1.15	ITT	Summary of Cardiovascular Risk Factors		SAC
1.16	ITT	Summary of Family History of Cardiovascular Risk Factors		SAC
1.17	ITT	Summary of COPD History at Screening	Include Duration of COPD and COPD type	SAC
1.18	ITT	Summary of COPD Exacerbation History at Screening		SAC

Study Population Tables				
No.	Popu- lation	Title	Programming Note	Deliverable
1.19	ITT	Summary of Smoking Status and History at Screening		SAC
1.20	ITT	Summary of Long-acting Bronchodilator Usage during the Run-in (Randomization Strata)		
1.21	ITT	Summary of Concomitant Medications Not Given for a COPD Exacerbation Taken Pre-Treatment		SAC
1.22	ITT	Summary of Concomitant Medications Not Given for a COPD Exacerbation Taken On-treatment		SAC
1.23	ITT	Summary of Concomitant Medications Not Given for a COPD Exacerbation Taken Post-treatment		
1.24	ITT	Summary of Concomitant Medications Given for a COPD Exacerbation Taken Pre-treatment		SAC
1.25	ITT	Summary of Concomitant Medications Given for a COPD Exacerbation Taken On-treatment		SAC
1.26	ITT	Summary of Concomitant Medications Given for a COPD Exacerbation Taken Post-treatment		SAC
Baseline Severity				
1.27	ITT	Summary of Screening Lung Function Test Results		SAC
1.28	ITT	Summary of GOLD Grade 1-4, GOLD CAT Category A-D and Reversibility at Screening		SAC
1.29	ITT	Summary of GOLD Grade 1-4, GOLD CAT Category A-D and Reversibility at Screening by Country		SAC
1.30	ITT	Summary of CAT Score at Screening		SAC
Compliance				
1.31	ITT	Summary of Device and Overall Percentage Treatment Compliance		SAC

10.8.4. Efficacy Tables

Efficacy: Tables				
No.	Population	Title	Programming Note	Deliverable
2.01	ITT	Summary of Baseline FEV1 (L)		SAC
2.02	ITT	Summary of Trough FEV1 (L)		SAC
2.03	ITT	Analysis of Trough FEV1 (L)		SAC
2.04	ITT	Covariance Parameter Estimates for Repeated Measures Analysis of Trough FEV1 (L)		SAC
2.05	ITT	Type III Tests of Fixed Effects for Repeated Measures Analysis of Trough FEV1 (L)		SAC
2.06	ITT	Significance Levels for Interactions of Treatment with Baseline FEV1, Geographical Region and Stratum for Trough FEV1 (L)		SAC
2.07	ITT	Analysis of Ratio (Trough FEV1/Baseline FEV1)		SAC
2.08	ITT	Summary of Baseline FVC (L)		SAC
2.09	ITT	Summary of Trough FVC (L)		SAC
2.10	ITT	Analysis of Trough FVC (L)		SAC
2.11	ITT	Summary of Baseline IC (L)		SAC
2.12	ITT	Summary of Trough IC (L)		SAC
2.13	ITT	Analysis of Trough IC (L)		SAC
BDI/TDI				
2.14	ITT	Summary of BDI Focal Score		SAC
2.15	ITT	Summary of TDI Focal Score		SAC
2.16	ITT	Analysis of TDI Focal Score		SAC
2.17	ITT	Summary and Analysis of Proportion of Responders According to TDI Focal Score		SAC
E-RS				
2.18	ITT	Summary of Four-Weekly Mean E-RS Total Score		SAC
2.19	ITT	Summary of Four-Weekly Mean E-RS Breathlessness Score		SAC

Efficacy: Tables				
No.	Population	Title	Programming Note	Deliverable
2.20	ITT	Summary of Four-Weekly Mean E-RS Cough and Sputum Score		SAC
2.21	ITT	Summary of Four-Weekly Mean E-RS Chest Score		SAC
2.22	ITT	Analysis of Four-Weekly Mean E-RS Total Score		SAC
2.23	ITT	Analysis of Four-Weekly Mean E-RS Breathlessness Score		SAC
2.24	ITT	Analysis of Four-Weekly Mean E-RS Cough and Sputum Score		SAC
2.25	ITT	Analysis of Four-Weekly Mean E-RS Chest Score		SAC
2.26	ITT	Summary and Analysis of Proportion of Responders According To E-RS Total Score		SAC
2.27	ITT	Summary and Analysis of Proportion of Responders According To E-RS Breathlessness Score		SAC
2.28	ITT	Summary and Analysis of Proportion of Responders According To E-RS Cough and Sputum Score		SAC
2.29	ITT	Summary and Analysis of Proportion of Responders According To E-RS Chest Score		SAC
SGRQ-C				
2.30	ITT	Summary of Baseline SGRQ Scores		SAC
2.31	ITT	Summary of SGRQ Total Score		SAC
2.32	ITT	Summary of SGRQ Symptoms Score		SAC
2.33	ITT	Summary of SGRQ Activity Score		SAC
2.34	ITT	Summary of SGRQ Impacts Score		SAC
2.35	ITT	Analysis of SGRQ Total Score		SAC
2.36	ITT	Summary and Analysis of Proportion of Responders According To SGRQ Total Score		SAC
CAT				
2.37	ITT	Summary of CAT Score	Include Baseline	SAC
2.38	ITT	Analysis of CAT Score		SAC
2.39	ITT	Summary and Analysis of Proportion of Responders According To CAT Score		SAC

Efficacy: Tables				
No.	Population	Title	Programming Note	Deliverable
COPD Exacerbations				
2.40	ITT	Summary of On-Treatment COPD Exacerbations		SAC
2.41	ITT	Summary of Post-Treatment COPD Exacerbations		SAC
2.42	ITT	Summary and Analysis of Time to First On-Treatment Mild/Moderate/Severe COPD Exacerbation		SAC
2.43	ITT	Summary and Analysis of Time to First On-Treatment Moderate/Severe COPD Exacerbation		SAC
2.44	ITT	Summary and Analysis of Time to First On-Treatment Severe COPD Exacerbation		SAC
2.45	ITT	Annual rate of on-treatment mild/moderate/severe exacerbations		SAC
2.46	ITT	Annual rate of on-treatment moderate/severe exacerbations		SAC
CID				
2.47	ITT	Summary of Deterioration and Individual Components	Include all composites	SAC
2.48	ITT	Summary and Analysis of Time to First Decrease from Baseline of ≥ 100 ml in Trough FEV1		SAC
2.49	ITT	Summary and Analysis of Time to First Increase from Baseline of ≥ 4 units in SGRQ Total Score		SAC
2.50	ITT	Summary and Analysis of Time to First Increase from Baseline of ≥ 2 units in CAT Score		SAC
2.51	ITT	Summary and Analysis of Time to First Decrease of ≥ 1 units in TDI		SAC
2.52	ITT	Summary and Analysis of Time to First Deterioration (SGRQ, FEV1, EXAC (mod/sev))		SAC
2.53	ITT	Summary and Analysis of Time to First Deterioration (CAT, FEV1, EXAC (mod/sev))		SAC
2.54	ITT	Summary and Analysis of Time to First Deterioration (CAT, SGRQ, TDI, EXAC (mod/sev))		SAC
2.55	ITT	Summary of Deterioration Status at Day 30		SAC
2.56	ITT	Analysis of Four-Weekly Mean E-RS Total Score by Day 30 Deterioration Status		SAC

Efficacy: Tables				
No.	Population	Title	Programming Note	Deliverable
2.57	ITT	Analysis of Mean Number of Inhalations of Rescue use per Day using e-Diary Day 30 Deterioration Status		SAC
2.58	ITT	Summary and Analysis of Time to First On-Treatment Moderate/Severe Exacerbation leading to hospitalisation by Day 30 Deterioration Status		SAC
2.59	ITT	Summary and Analysis of Time to Mortality by Day 30 Deterioration Status		SAC
Rescue Use				
2.60	ITT	Summary of Mean Number of Inhalations of Rescue Medication per Day using e-Diary		SAC
2.61	ITT	Analysis of Mean Number of Inhalations of Rescue Medication per Day over Weeks 1-24 using e-Diary		SAC
2.62	ITT	Summary of Percentage of Rescue-Free Days using e-Diary		SAC
2.63	ITT	Analysis of Percentage of Rescue-Free Days over Weeks 1-24 using e-Diary		SAC
2.64	ITT	Summary of Mean Number of Occurrences of Rescue Medication per Day using eMDI.		SAC
2.65	ITT	Analysis of Mean Number of Occurrences of Rescue Medication per Day over Weeks 1-24 using eMDI		SAC
2.66	ITT	Summary of Percentage of Rescue-Free Days using eMDI		SAC
2.67	ITT	Analysis of Percentage of Rescue-Free Days over Weeks 1-24 using eMDI		SAC
Subject Global Ratings				
2.68	ITT	Summary of Subject Global Rating of COPD Severity		SAC
2.69	ITT	Summary and Analysis of Subject Global Rating of Change in COPD Severity	Use gsk2834425/ctt116853 as reference	SAC
Physical Activity Monitor				
2.70	AM	Summary of Weekly Mean Step Count		SAC

Efficacy: Tables				
No.	Population	Title	Programming Note	Deliverable
2.71	AM	Analysis of Weekly Mean Step Count		SAC
2.72	AM	Summary of Weekly Mean Duration of Light Physical Activity (Hours)		SAC
2.73	AM	Analysis of Weekly Mean Duration of Light Physical Activity (Hours)		SAC
2.74	AM	Summary of Weekly Mean Duration of Moderate to Vigorous Physical Activity (Hours)		SAC
2.75	AM	Analysis of Weekly Mean Duration of Moderate to Vigorous Physical Activity (Hours)		SAC
2.76	AM	Summary of Weekly Mean Total Energy Expenditure (kCal)		SAC
2.77	AM	Analysis of Weekly Mean Total Energy Expenditure (kCal)		SAC

10.8.5. Efficacy Figures

Efficacy: Figures				
	Population	Title	Programming Note	Deliverable
Spirometry				
2.01	ITT	Box Plot of Change from Baseline in Trough FEV1 (L) at Week 24		SAC
2.02	ITT	Empirical Distribution Function Plot of Change from Baseline in Trough FEV1 (L) at Week 24		SAC
2.03	ITT	Least Squares Mean (95% CI) Change from Baseline in Trough FEV1 (L)		SAC
2.04	ITT	Least Squares Mean (95% CI) Treatment Difference in Change from Baseline in Trough FEV1 (L)		SAC
2.05	ITT	Least Squares Mean (95% CI) Change from Baseline in Trough FVC (L)		SAC
2.06	ITT	Least Squares Mean (95% CI) Treatment Difference in Change from Baseline in Trough FVC (L)		SAC
2.07	ITT	Least Squares Mean Change from Baseline (95% CI) in Trough IC (L)		SAC

Efficacy: Figures				
	Popu- lation	Title	Programming Note	Deliverable
2.08	ITT	Least Squares Mean (95% CI) Treatment Difference in Change from Baseline in Trough IC (L)		SAC
BDI/TDI				
2.09	ITT	Least Squares Means (95% CI) TDI Focal Score		SAC
2.10	ITT	Least Squares Mean (95% CI) Treatment Difference in Change from Baseline in TDI Focal Score		SAC
E-RS				
2.11	ITT	Least Squares Mean Change from Baseline (95% CI) in Four-Weekly Mean E-RS Total Score		SAC
2.12	ITT	Least Squares Mean (95% CI) Treatment Difference in Change from Baseline in Four-Weekly Mean E-RS Total Score		SAC
2.13	ITT	Least Squares Mean Change from Baseline (95% CI) in Four-Weekly Mean E-RS Breathlessness Score		SAC
2.14	ITT	Least Squares Mean (95% CI) Treatment Difference in Change from Baseline in Four-Weekly Mean E-RS Breathlessness Score		SAC
2.15	ITT	Least Squares Mean Change from Baseline (95% CI) in Four-Weekly Mean E-RS Cough and Sputum Score		SAC
2.16	ITT	Least Squares Mean (95% CI) Treatment Difference in Change from Baseline) in Four-Weekly Mean E-RS Cough and Sputum Score		SAC
2.17	ITT	Least Squares Mean Change from Baseline (95% CI) in Four-Weekly Mean E-RS Chest Score		SAC
2.18	ITT	Least Squares Mean (95% CI) Treatment Difference in Change from Baseline in Four-Weekly Mean E-RS Chest Score		SAC
SGRQ				
2.19	ITT	Least Squares Mean (95% CI) Change from Baseline in SGRQ Total Score		SAC
2.20	ITT	Least Squares Mean (95% CI) Treatment Difference in Change from Baseline in SGRQ Total Score		SAC

Efficacy: Figures				
	Popu- lation	Title	Programming Note	Deliverable
CAT				
2.21	ITT	Least Squares Mean Change from Baseline (95% CI) in CAT Score		SAC
2.22	ITT	Least Squares Mean (95% CI) Treatment Difference in Change from Baseline) in CAT Score		SAC
COPD Exacerbations				
2.23	ITT	Kaplan-Meier Plot of Time to First On-Treatment Mild/Moderate/Severe COPD Exacerbation (Days)		SAC
2.24	ITT	Kaplan-Meier Plot of Time to First On-Treatment Moderate/Severe COPD Exacerbation (Days)		SAC
2.25	ITT	Kaplan-Meier Plot of Time to First On-Treatment Severe COPD Exacerbation (Days)		SAC
CID				
2.26	ITT	Kaplan-Meier Plot of Time to First Decrease from Baseline of ≥ 100 ml in Trough FEV1		SAC
2.27	ITT	Kaplan-Meier Plot of Time to First Increase from Baseline of ≥ 4 units in SGRQ Total Score		SAC
2.28	ITT	Kaplan-Meier Plot of Time to First Increase from Baseline of ≥ 2 units in CAT Score		SAC
2.29	ITT	Kaplan-Meier Plot of Time to First Decrease of ≥ 1 units in TDI		SAC
2.30	ITT	Kaplan-Meier Plot of Time to First Deterioration (SGRQ, FEV1, EXAC (mod/sev)) (Days)		SAC
2.31	ITT	Kaplan-Meier Plot of Time to First Deterioration (CAT, FEV1, EXAC (mod/sev)) (Days)		SAC
2.32	ITT	Kaplan-Meier Plot of Time to First Deterioration (CAT, SGRQ, TDI, EXAC (mod/sev)) (Days)		SAC
2.33	ITT	Kaplan-Meier Plot of Time to First On-Treatment Moderate/Severe Exacerbation Leading to Hospitalisation by Day 30 Deterioration Status		SAC
2.35	ITT	Kaplan-Meier Plot of Time to Mortality by Day 30 Deterioration Status		SAC
Rescue Use				
2.36	ITT	Least Squares Mean (95% CI) Treatment Difference in Change from Baseline in Mean Number of Inhalations of Rescue Medication per Day over Weeks 1-24 using e-Diary		SAC

Efficacy: Figures				
	Popu- lation	Title	Programming Note	Deliverable
2.37	ITT	Least Squares Mean (95% CI) Change from Baseline in Percentage of Rescue-Free Days over Weeks 1-24 using e-Diary		SAC
2.38	ITT	Least Squares Mean (95% CI) Treatment Difference in Change from Baseline in Mean Number of Occurrences of Rescue Medication per Day over Weeks 1-24 using eMDI		SAC
2.39	ITT	Least Squares Mean (95% CI) Change from Baseline in Percentage of Rescue-Free Days over Weeks 1-24 using eMDI		SAC
Physical Activity Monitor				
2.40	ITT	Histograms of Change from Baseline in Weekly Mean Step Count at Week 1, Week 4 and Week 24 by Treatment Group		SAC
2.41	ITT	Histograms of Change from Baseline in Weekly Mean Duration of Light Physical Activity (Hours) at Week 1, Week 4 and Week 24 by Treatment Group		SAC
2.42	ITT	Histograms of Change from Baseline in Weekly Mean Duration of Moderate to Vigorous Physical Activity (Hours) at Week 1, Week 4 and Week 24 by Treatment Group		SAC
2.43	ITT	Histograms of Change from Baseline in Weekly Mean Total Energy Expenditure (kCal) at Week 1, Week 4 and Week 24 by Treatment Group		SAC
2.44	ITT	Least Squares Mean (95% CI) Change from Baseline in Weekly Mean Step Count		SAC
2.45	ITT	Least Squares Mean (95% CI) Change from Baseline in Weekly Mean Duration of Light Physical Activity (Hours)		SAC
2.46	ITT	Least Squares Mean (95% CI) Change from Baseline in Weekly Mean Duration of Moderate to Vigorous Physical Activity (Hours)		SAC
2.47	ITT	Least Squares Mean (95% CI) Change from Baseline in Weekly Mean Total Energy Expenditure (kCal)		SAC

10.8.6. Safety Tables

Safety Tables				
No.	Popu- lation	Title	Programming Note	Deliverable
Exposure				
3.01	ITT	Summary of Exposure		SAC
Adverse Events				
3.02	ITT	Overview of Adverse Events		SAC
3.03	ITT	Summary of On-treatment Adverse Events by System Organ Class and Preferred Term		SAC
3.04	ITT	Summary of Post-treatment Adverse Events by System Organ Class and Preferred Term		SAC
3.05	ITT	Summary of On-treatment Drug-Related Adverse Events by System Organ Class and Preferred Term		SAC
3.06	ITT	Summary of Pre-treatment Serious Adverse Events by System Organ Class and Preferred Term		SAC
3.07	ITT	Summary of On-treatment Serious Adverse Events by System Organ Class and Preferred Term		SAC
3.08	ITT	Summary of On-treatment Fatal Serious Adverse Events by System Organ Class and Preferred Term		SAC

Safety Tables				
No.	Population	Title	Programming Note	Deliverable
3.09	ITT	Summary of On-treatment Serious Adverse Events (Serious, Drug-Related Serious and Fatal) by System Organ Class and Preferred Term (Number of Subjects and Occurrences)		SAC
3.10	ASE	Summary of Pre-treatment Adverse Events Leading Withdrawal from the Study by System Organ Class and Preferred Term		SAC
3.11	ITT	Summary of On-treatment Drug-related Serious Adverse Events by System Organ Class and Preferred Term		SAC
3.12	ITT	Summary of On-treatment Drug-related Fatal Serious Adverse Events by System Organ Class and Preferred Term		SAC
3.13	ITT	Summary of On-treatment Adverse Events Leading to Permanent Discontinuation of Study Treatment or Withdrawal from the Study by System Organ Class and Preferred Term		SAC
3.14	ITT	Summary of On-treatment Adverse Events of Special Interest		SAC
3.15	ITT	Summary of On-treatment Serious Adverse Events of Special Interest		SAC
3.16	ASE	Relationship between Adverse Event System Organ Class, Preferred Term and Verbatim Text		SAC
3.17	ITT	Summary of Common ($\geq 3\%$) On-treatment Non-Serious Drug-related Adverse Events by System Organ Class and Preferred Term (Number of Subjects and Occurrences)		SAC

Safety Tables				
No.	Popu- lation	Title	Programming Note	Deliverable
3.18	ITT	Summary of Common (>=3%) On-treatment Serious Adverse Events by Overall Frequency		SAC
3.19	ITT	Summary of Common (>=3%) On-treatment Serious Drug-related Adverse Events by Overall Frequency		SAC
3.20	ITT	Summary of the 10 Most Frequent On-treatment Adverse Events in Each Treatment Group		SAC
3.21	ITT	Summary of On-treatment Adverse Events by System Organ Class, Preferred Term and Age Subgroup		SAC
3.22	ITT	Summary of On-treatment Adverse Events by System Organ Class and Preferred Term and Maximum Intensity		SAC
3.33	ITT	Summary of On-treatment Drug-Related Adverse Events by System Organ Class and Preferred Term and Maximum Intensity		SAC

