8. SAFETY ANALYSES

The safety analyses will be based on the ITT population, unless otherwise specified. Data collected after completion or withdrawal of study treatment will be considered post-treatment and included in relevant displays.

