10. APPENDICES

10.1. Appendix 1: Schedule of Activities

10.1.1. Protocol Defined Schedule of Events

			Blinded Treatment					
Visit	Pre-screen ¹ 0	Screen/ Run-in 1	Rando- mization 2	3	4	5	EW Visit ²	Telephone Follow up contact 6
Week	-10 to -4	-4	0	4	12	24		
Day	-70 to -28	-28	1	28	84	168		7 days after V5 or EW Visit
Window	-7/+2 days	-7/+2 days	-7/+2 days	-7/+2 days	-7/+2 days	-7/+2 days		±3 days
Screen/Baseline								
Informed consent	X							
Demography	X							
Medical/COPD history		X						
Smoking history/status		X						
Smoking cessation counselling		X						
Concomitant medication assessment	X	X	X	X	X	X	X	X
Height and weight		X						
Cardiovascular History/family history of premature CV disease)		X						
Screening spirometry (including post bronchodilator testing) ³		X						
CAT questionnaire		X	X					
Verify Inclusion/Exclusion Criteria		X						
Training on use of inhalers		X	X					
Training on use of eDiary and eMDI		X	X					
Verify randomization Criteria			X					

			Blinded Treatment					
Visit	Pre-screen ¹ 0	Screen/ Run-in 1	Rando- mization 2	3	4	5	EW Visit ²	Telephone Follow up contact 6
Week	-10 to -4	-4	0	4	12	24		
Day	-70 to -28	-28	1	28	84	168		7 days after V5 or EW Visit
Window	-7/+2 days	-7/+2 days	-7/+2 days	-7/+2 days	-7/+2 days	-7/+2 days		±3 days
Register Visit in InForm	X	X	X	X	X	X	X	X
Register Visit in RAMOS NG	X	X	X	X	X	X	X	X
Efficacy/HRQoL assessments								
Spirometry, including pre-dose FEV ₁ , trough FEV ₁ and inspiratory capacity			X	X	X	X		
SAC BDI questionnaire ⁴			X					
SAC TDI questionnaire ⁴				X	X	X		
SGRQ-C questionnaire ⁴			X	X	X	X		
CAT questionnaire ⁴		X	X	X	X	X		
EXACT/ER-S: COPD ⁵		—————→						
Patient Global Rating of COPD severity			X	X	X	X		
Patient Global Rating of Change in COPD				X	X	X		
Safety assessments								
Adverse events/Serious adverse events ⁶	X	X	X	X	X	X	X	X
COPD exacerbation assessment	X	X	X	X	X	X	X	X
12-Lead ECG		X						
Urine pregnancy test ⁷		X	X			X	X	
Pharmacogenetic sample ⁸			←———— X —————→					
Medication/Supplies								
Dispense rescue albuterol/slabutamol. Dispense MDI ⁹		X	X	X	X	X		
Assess COPD medication compliance ¹⁰ during run-in			X					
Dispense eDiary		X						
Assess compliance with eDiary during run-in			X					
Collect rescue albuterol/slabutamol.			X	X	X	X	X	

			Blinded Treatment					
Visit	Pre-screen ¹ 0	Screen/ Run-in 1	Rando- mization 2	3	4	5	EW Visit ²	Telephone Follow up contact 6
Week	-10 to -4	-4	0	4	12	24		

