10.3. Appendix 3: Study Phases and Treatment Emergent Adverse Events

10.3.1. Study Phases for Concomitant Medication

The following rules will be used to classify a concomitant medication as being taken during one or more study treatment phases (pre-treatment, on-treatment and post-treatment):

Study Phase	Definition		
	Pre-Treatment	On-Treatment	Post-Treatment
Subject did not take study treatment (e.g, screen failures) and conmed stop date > date of Screening or variable that asks if conmed is on-going (refer hereafter as goingmed) is "yes"	Y		
(Conmed start date < treatment start date or variable that asks if medication taken prior to study is "yes" (refer hereafter as priormed)) and date of Screening < conmed stop date < treatment start date	Y		
(Conmed start date < treatment start date or priormed is yes) and treatment start date ≤ conmed stop date ≤ treatment stop date	Y	Y	
(Conmed start date < treatment start date or priormed is yes) and (conmed stop date > treatment stop date or goingmed is "yes")	Y	Y	Y
(Treatment start date ≤ conmed start date < treatment stop date and treatment start date ≤ conmed stop date ≤ treatment stop date) or (Treatment start date = conmed start date = conmed stop date = treatment stop date)		Y	
([Treatment start date ≤ conmed start date < treatment stop date] or [Treatment start date = conmed start date = treatment stop date]) and (conmed stop date > treatment stop date or goingmed is Yes)		Y	Y
Conmed start ≥ treatment stop date and treatment start date ≠ treatment stop date			Y

1. NOTES:

- The duration of a single concomitant medication can extend over multiple study phases
- Please refer to [Appendix 6: Reporting Standards for Missing Data](#) for handling of partial dates for concomitant medication.
- Note: If priormed or goingmed flags are missing or inconsistent, then medications will be assigned to all applicable phases.

10.3.2. Study Phases for Adverse Events and All Other Data Recorded in Logs (excluding Concomitant Medications)

Study Phase	Definition
Pre-Treatment	Date < Study Treatment Start Date
On-Treatment	Study Treatment Start Date ≤ Date ≤ Study Treatment Stop Date + 1
Post-Treatment	Date > Study Treatment Stop Date + 1

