10.3.3. Treatment Emergent Flag for Adverse Events and Exacerbations

Flag	Definition
Treatment Emergent	
 If AE onset date is on or after treatment start date & on or before treatment stop date plus one day. Study Treatment Start Date ≤ AE Start Date ≤ Study Treatment Stop Date + 1.

NOTES:

- If the study treatment stop date is missing, then the AE will be considered to be On-Treatment.
- Time of study treatment dosing and start/stop time of AEs should be considered, if collected.

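### SAEs, fatal SAEs and special-interest AEs that start more than one day after treatment stop have no dedicated by-arm summary table

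*SAP*

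**What the plan says.** SAP Section 10.3.2 defines the on-treatment phase for adverse events as "Study Treatment Start Date ≤ Date ≤ Study Treatment Stop Date + 1" and the post-treatment phase as "Date > Study Treatment Stop Date + 1". Section 10.3.3 ties the treatment-emergent flag to onset: "If AE onset date is on or after treatment start date & on or before treatment stop date plus one day".

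The schedule in Section 10.1.1 marks AE and SAE collection at every visit, including the Early Withdrawal (EW) visit and the telephone follow-up. That call is timed "7 days after V5 or EW Visit", with a window of ±3 days. The EW visit has no fixed day; a footnote asks only that it take place promptly.

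Section 8 states: "Data collected after completion or withdrawal of study treatment will be considered post-treatment and included in relevant displays". It does not say which displays those are.

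In Section 10.8.6 the fatal-event table (3.08) is "Summary of On-treatment Fatal Serious Adverse Events by System Organ Class and Preferred Term". The only SAE table outside the on-treatment phase is 3.06, "Summary of Pre-treatment Serious Adverse Events by System Organ Class and Preferred Term". Table 3.04 covers post-treatment AEs of all kinds by system organ class and preferred term. Table 3.02 is an overview of AEs with no phase in its title.

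**The concern.** The trial compares a LAMA/LABA combination with each class alone. Cardiac and respiratory events shortly after stopping treatment are therefore part of the safety picture, above all in subjects who stop early. An SAE or fatal event that starts two or more days after the last dose is collected, but no table is specified to count it by arm as serious, fatal or of special interest.

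The display list looks like an omission rather than a deliberate choice. The SAP plans post-treatment tables for all AEs (3.04), COPD exacerbations (2.41) and concomitant medications (1.23, 1.26), and it gives pre-treatment SAEs their own table. Post-treatment SAEs, fatal SAEs and special-interest AEs (AESIs) are left out. A report built strictly from the list would give SAE and death counts by arm that are incomplete for the period in which the data were collected.

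**Working it through.** The plan states no figure to reproduce. The check is a count of table titles and some day arithmetic.

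**Titles naming serious, fatal or special-interest events**
- Main list (10.8.6): 3.06, 3.07, 3.08, 3.09, 3.11, 3.12, 3.14, 3.15, 3.18, 3.19, which is 10 tables. Nine are on-treatment, one (3.06) is pre-treatment and none is post-treatment.
- Maintenance-naive safety list: 3.38, 3.39, 3.41, 3.42, which is 4 tables, all on-treatment. This list has no counterpart to Table 3.04.
- Total: 10 + 4 = 14, of which 9 + 4 = 13 are on-treatment, 1 is pre-treatment and 0 are post-treatment.

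**Where a later-onset event does appear**
- Table 3.04: counted by preferred term, not marked as serious or fatal. AESI groups are built from SMQs and sponsor-defined term sets (10.5.4), so subject counts per AESI group cannot be read from it.
- Table 2.41 (2.103 for maintenance-naive): post-treatment exacerbations, with no severity split stated in the title.
- Listings 34 (non-fatal SAEs), 35 (fatal SAEs) and 56 (all-cause deaths): no phase limit in the titles, and Section 8.1 requires AE and SAE listings to show the phase. These give individual lines, not counts by arm.
- Table 3.02: no phase limit in the title, content not specified.

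**Length of the uncovered period**

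Let k be the days from treatment stop to Visit 5 or the EW visit, and f the days from that visit to the call (4, 7 or 10). The on-treatment phase covers one day after stop, so the gap is k + f − 1 days.

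For a completer, assume the last dose is at Visit 5 on Day 168, so k = 0. On-treatment runs to Day 169.
- f = 7: call on Day 175, gap Days 170–175 = 6 days, 6/175 = 3.4%.
- f = 4: call on Day 172, gap = 3 days, 3/172 = 1.7%.
- f = 10: call on Day 178, gap = 9 days, 9/178 = 5.1%.

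For an early stopper, each day between treatment stop and the EW visit adds one day, and the SAP sets no upper limit on k. Section 2.3 expects 2424 − 2181 = 243 randomised subjects not to complete (243/2424 = 10.0%). That is how many could have a longer gap, not how many will have an event in it.

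**The case against.** The strongest reply is that nothing is lost. Post-treatment AEs are tabulated in 3.04, exacerbations in 2.41, and every SAE and death is listed. Section 8 promises relevant displays, not an SAE-specific table, so no stated rule is broken. This stands: the point concerns an incomplete set of summaries, not a contradiction. It does not supply the missing counts by arm.

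A second reply is that Table 3.02 may already show serious and fatal events in all phases. It may; its content follows sponsor standards that the SAP does not reproduce. It therefore cannot be said that no by-arm display of later-onset serious events will exist, only that none is specified.

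Some stronger readings are tempting and are not supported:
- A reader might infer that every SAE or death collected during follow-up is left out. Phase follows onset, so an event that starts by stop + 1 day and is reported, or becomes fatal, later still counts in 3.07 or 3.08.
- A reader might express the gap as a share of the follow-up days, which gives a large percentage. The denominator is then a tail of a few days; as a share of a completer's observation the gap is small.
- A reader might cite Table 3.13 (AEs leading to discontinuation or withdrawal). An AE that causes treatment to stop ordinarily starts on treatment, so that table is a poor example.
- A reader might expect deaths in Table 3.08 to reconcile with Table 2.59, "Summary and Analysis of Time to Mortality by Day 30 Deterioration Status". Under Section 7.3.5.1 that analysis covers deaths after Day 30 and compares deterioration groups rather than arms. It answers another question and need not match.

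**Conclusion.** The point holds in limited form. Following the display list, SAEs, fatal SAEs and AESIs with onset more than one day after treatment stop receive no dedicated by-arm summary, and no table is specified to give total deaths by randomised arm. The uncovered time is about 3 to 9 days for a completer, assuming the last dose is at Visit 5 on Day 168; an earlier last dose lengthens it by the same number of days. It can be longer after early discontinuation.

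A reader might infer that the omission biases the comparison between arms. That would require early stopping, or event risk after stopping, to differ by arm, and the SAP gives no figure for either. Unequal omission is possible, not shown. The primary efficacy result is unaffected. This is an inexpensive improvement in the completeness of safety reporting that should be made before unblinding, not the correction of an erroneous rule.

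**What to change.** - Add on-treatment, post-treatment and total columns to Tables 3.07, 3.08, 3.14 and 3.15, or add post-treatment versions of them, by randomised arm.
- Add a table of all deaths by randomised arm from first dose to last contact.
- State what Table 3.02 contains. If it shows serious and fatal events by phase, saying so would close part of the gap, though not the AESI part.
- Keep on-treatment as the main presentation and leave the phase definitions unchanged.

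The cost is a few extra tables or columns from data and phase flags that already exist. The one downside is that total SAE and death counts may look slightly less favourable than the on-treatment counts alone.
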